15.11 FINANCIAL DISCLOSURE

Regulation requires sponsors to obtain financial information from investigators participating in covered clinical studies. Each Principal Investigator and Sub-Investigator is required to provide financial disclosure information and to promptly update Obagi with any relevant changes to their financial information throughout the course of the clinical study and for up to one year after its completion.

15.12 INVESTIGATOR AND SITE QUALIFICATIONS; DEBARMENT

Persons debarred from conducting or working in clinical studies by any court or regulatory agency will not be allowed to conduct or work on the study. The investigator will immediately disclose in writing if any person who is involved in conducting the study is debarred or if any proceeding for debarment is pending or, to the best of the investigator's knowledge, threatened. To that end, the investigator has not been personally and will not use as an assistant any person who is debarred from participation in clinical trials under the Generic Drug Enforcement Act of 1992 (21 USC § 301 et seq.) or any other provision of law (e.g., 21 CFR § 312.70). If such a proceeding should commence, involving the investigator or any assistant, the investigator will promptly inform Obagi. Further, the investigator has not and no person or entity affiliated with the investigator or under the investigator's supervision is excluded from participation in a Federal Health Care Program as defined in 42 U.S.C. § 1320a. The investigator has never been convicted of a felony.

The investigator will provide a signed, accurate, non-misleading, and current copy of his or her curriculum vitae to Obagi that demonstrates his or her qualifications to conduct this study and, if requested, will provide a list of sub-investigators or health professionals who are assisting in the conduct of this study and documentation of their qualifications.

The facilities where this study will be conducted have the necessary subject population and personnel to properly conduct the study.

APPENDIX 1: INSTRUCTION FOR APPLICATION OF STUDY PRODUCT

Please follow these instructions carefully. Contact the study staff at the telephone number noted below if you have any questions about the study:

Contact:	Telephone:

Morning Cleansing and Application Day Cream with SPF: once a day in the am (morning)

- STEP 1: Wet face and hands with lukewarm water. Dispense a full 1-pump dose of the Exfoliating Cleanser into the palm of your hand and gently rub over your entire face, taking care to avoid the eyes. Rinse completely with lukewarm water and gently pat your face dry with a towel.
- STEP 2: Using your fingertips, apply a full 1-pump dose of the Moisturizer to the entire face and forehead, avoiding the eye area.

Evening Cleansing and Application Night Cream: once a day in the pm (evening)

- STEP 1: Thoroughly remove all eye makeup. Wet face and hands with lukewarm water.

 Dispense a full 1-pump dose of the Exfoliating Cleanser into the palm of your hand and gently rub over your entire face, taking care to avoid the eyes. Rinse completely with lukewarm water and gently pat your face dry with a towel.
- STEP 2: Using your fingertip, gently a full 1-pump dose of the Night Cream to the entire face and forehead, avoiding the eye area.

For all products, avoid contact with eyes. Rinse eyes thoroughly if contact occurs.

APPENDIX 2: SUBJECT'S SELF-ASSESSMENT OF IMPROVEMENT

Questionnaire – Day 14 and Day 28

SUBJECT QUESTIONNAIRE - SELF-ASSESSMENT OF IMPROVEMENT					
(THE SUBJECT SHOULD COMPLETE THIS QUESTIONNAIRE AND INITIAL THE BOTTOM OF THIS PAGE IN THEIR OWN HANDWRITING)					
Have you noticed an improvement to your skin appearance? ☐ Yes ☐ No					
If Yes, please rate the speed with which you saw an improvement in your facial skin:					
When: Immediately Within 1 day Within 2 weeks Within 4 weeks					
Subject to Initial:					

APPENDIX 3: SUBJECT'S SELF-ASSESSMENT (PART 1)

Questionnaire – Day 14, 28, 56 and 84/EOS

SUBJECT'S SELF-ASSESSMENT QUESTIONNAIRE (PART 1)

(THE SUBJECT SHOULD COMPLETE THIS QUESTIONNAIRE AND INITIAL THE BOTTOM OF THIS PAGE IN THEIR OWN HANDWRITING)

For each question, please put a check mark ($\sqrt{}$) in the column you agree with the most, use one check mark for each statement.

Please rate your agreement with the following statements:

	Strongly Agree	Agree	Indifferent	Disgree	Strongly Disagree
I am satisfied with the overall results this product provides					
My lines and wrinkles are less visible					
My face appears more firm					
My skin tone has become more even					
My skin brightness has increased					
My skin texture has improved					
My skin looks refreshed					
My skin feels more resilient					

Subject to Initia	al:
-------------------	-----

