
Test product, dose and mode of administration:

Obagi 360 System consisting of: Obagi 0.5% retinol, Hydrafactor SPF30, and Exfoliating cleanser. The system will be used once daily for 3 months.

Reference therapy, dose and mode of administration:

None

Duration of treatment, enrollment and follow-up:

Duration of treatment period: 12 weeks

Criteria for evaluation:

- 1. Improvement in manifestations of photodamage assessed by the investigator using the Investigator's Skin Grading Assessment.
- 2. Assessment of improvement by the subject using the Subject's Self-Assessment.

Safety:

Safety variables include treatment-emergent adverse events (AEs), serious AEs (SAEs), treatment related AEs, and AEs leading to study discontinuation.

The investigator will assess the tolerability of the product at each visit.

Sample size:

Forty subjects will be enrolled. Forty (40) subjects are adequate to obtain information on the anti-aging effects of the Obagi 360 system.

Statistical methods:

The effect of the Obagi 360 system on photodamage will be evaluated using the Investigator's Skin Grading System. The changes from baseline in the scores will be summarized and tested for significance using the paired T-test for each time point. In addition, a summary of the distribution or scores (improvement or worsening) will be summarized and categorized as the number and proportion of subjects "Improved", "Equal to" or "Worse" than baseline.

For the Subject's Self-Assessment, the response to each question will be summarized by the proportion of subjects in each category. No statistical testing will be performed on the Subject's Self-Assessment.

Safety will be summarized by the incidence of adverse events over the study by body system and preferred term. The tolerability will be summarized by the proportion of subjects with none, mild, moderate, and severe for each assessment by visit.

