7.1 STUDY DESIGN OVERVIEW

This is an open-label study of the Obagi 360 system used daily for 3 months to evaluate the effects on photodamage. Subjects will be evaluated at five time points; a baseline visit and at 2, 4, 8, and 12 weeks. The total study duration will be 12 weeks for each subject.

At the baseline visit (Day 0) the subject will complete the informed consent and photo release and will be evaluated for eligibility. Eligible subjects will be assigned a subject number and enrolled. At the baseline visit photographs will be taken and the investigator will complete the skin grading assessment. The subject will be instructed in the use of the product. The subjects will return to clinic on Days 14, 28, 56, and 84 (\pm 5 days) to assess response. At each visit photographs will be obtained and the investigator will complete the skin grading assessment. Additionally, the subject will complete a self-assessment at subsequent visits.

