14.2.4 ANALYSIS OF SUBJECT'S SELF-ASSESSMENT

For the Subject's Self-Assessment, each question will be summarized separately using the proportion of subjects replying for each category (e.g., Strongly agree, Agree, Indifferent, Disagree, Strongly disagree) by visit. No statistical testing will be performed on the Subject's Self-Assessment.

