Appendix 3: Subject's Self-Assessment

(PART 2)

Questionnaire – Day 14, 28, 56 and 84/EOS

SI	JBJECT'S	SELF-A	SSESSMENT	QUESTIONNAIRE ((PART 2)
	JUJULU I		COLUCIAL	Q C E D I I C I II II II II I	TILLE W/

(THE SUBJECT SHOULD COMPLETE THIS QUESTIONNAIRE AND INITIAL THE BOTTOM OF THIS PAGE IN THEIR OWN HANDWRITING)

For each question, please put a check mark ($\sqrt{}$) in the column you agree with the most, use one check mark for each statement.

Please rate your agreement with the following statements:

	Strongly Agree	Agree	Indifferent	Disagree	Strongly Disagree
My skin clarity has improved					
My face feels rejuvenated					
My skin has a youthful glow/radiance					
My skin vitality has increased					
My skin looks and feels more hydrated					
My pores are less visible					
My breakouts are less visible					
My breakouts are less frequent					
My skin looks and feel smoother					

Would you recommend this product to a friend?	□Yes	□No
Would you want to purchase this product?	□Yes	□No
Would you continue using this product if made available?	□Yes	□No

Subject	in	initial.	

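### Appendix 3's comparative statements name no comparison point, so the by-visit agreement rates cannot be read unambiguously as improvement since the start of treatment

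*Protocol*

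**What the plan says.** The Synopsis lists the subject's own assessment of improvement as the second of two criteria for evaluation. Under Section 11.3 and Table 1 it is collected only after baseline.

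The instrument is printed in Appendix 3, in two parts, both labelled for Days 14, 28, 56 and 84/EOS. The instruction reads "Please rate your agreement with the following statements". The statements that follow include "My lines and wrinkles are less visible" in Part 1 and "My breakouts are less frequent" in Part 2. Part 1 opens with a satisfaction item, "I am satisfied with the overall results this product provides". Part 2 ends with three Yes/No items, the first being "Would you recommend this product to a friend".

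For the analysis, Section 14.2.4 states that "each question will be summarized separately using the proportion of subjects replying for each category", by visit, with no statistical testing.

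The Synopsis describes the test article as "Obagi 360 System consisting of: Obagi 0.5% retinol, Hydrafactor SPF30, and Exfoliating cleanser". Section 7.1 refers to the same system in the singular: "The subject will be instructed in the use of the product".

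**The concern.** A statement that something is less visible, more even or less frequent has a definite meaning only if the respondent knows what it is compared with. At Day 14 the start of treatment is the natural reference, because no earlier post-baseline visit exists. From Day 28 on there are at least two candidates: the start of the study and a more recent visit.

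The answers are the whole result for this criterion, and they are tabulated by visit, so a reader will tend to take them as a time course of improvement. If some subjects answer against a recent visit, the table mixes total change with recent change. There is no baseline self-rating and no record of the reference each subject used, so no later analysis can separate the two.

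**Working it through.** The protocol gives no figure to reproduce here. The check is a count of the items, followed by a comparison of sections.

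**Item count, Appendix 3**

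| | Part 1 | Part 2 | Total |
|---|---|---|---|
| Agreement statements | 8 | 9 | 17 |
| Comparative | 6 | 7 | 13 |
| Describing a state (refreshed, rejuvenated, youthful glow) | 1 | 2 | 3 |
| Overall satisfaction | 1 | 0 | 1 |
| Yes/No items | 0 | 3 | 3 |

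- Comparative in Part 1: lines and wrinkles, firmness, evenness of tone, brightness, texture, resilience.
- Comparative in Part 2: clarity, vitality, hydration, pores, visibility of breakouts, frequency of breakouts, smoothness.
- Comparative statements that give a comparison point: 0 of 13.
- Items that say *this product*: 1 satisfaction + 3 Yes/No = 4 of 20. Among the 13 comparative statements: 0.

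The missing reference and the product wording are therefore separate points and affect different items.

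**How the protocol treats the investigator's grading.** Section 11.1 gives the investigator a static scale, to be scored without looking back at earlier grades. Section 14.2.3 then compares each visit with baseline. The reference is fixed by design. Appendix 3 asks the subject to judge change directly but gives her no equivalent instruction.

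**What follows for one subject.** Suppose her skin has improved by Day 28 and stays the same to Day 56. Against study start, she agrees at both visits. Against Day 28, she can truthfully answer Indifferent or Disagree at Day 56. Her skin is the same, but her answer falls into another column of the table.

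**Size.** If a proportion *p* has improved and kept the gain, and a fraction *f* of these answer against a recent visit, the apparent fall in agreement is *p* × *f*. The protocol gives neither *p* nor *f*. Purely as an assumption, *p* = 60% and *f* = 10% to 25% give 0.60 × 0.10 = 6 points to 0.60 × 0.25 = 15 points. This shows how the effect works; it is not an estimate.

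**Appendix 2.** This form is used only at Days 14 and 28. It asks how soon improvement was noticed, with options from immediately to within four weeks. Those options make natural sense only when counted from first use, so the form already implies its reference point.

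**The case against.** The strongest reply is that the context already points to the start of use. The form opens by asking about the overall results the product provides, several statements have cumulative wording (has increased, has improved), and nothing mentions a previous visit or says that earlier answers are shown. The summaries are untested and drive neither the sample size nor a decision. The protocol specifies a comparison with baseline only for the investigator's scores. Much of this stands: reading against the last visit is possible, not demonstrated, and the consequence is limited. It does not remove the ambiguity from Day 28 on, and the Synopsis does present the self-assessment as a measure of improvement.

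Three stronger readings are tempting and are not supported:

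- *The rates cannot be read as change from the start at all.* They can, and many subjects may answer that way. The fault is that the reader cannot tell who did.
- *The artefact is about 15 points, as large as the sampling error.* The half-width for one proportion of 60% at n = 40 is 1.96 × √(0.6 × 0.4 / 40) = 15.2 points. But 15 points is only the top of an assumed range, and the precision of a single proportion is the wrong yardstick for a fall between visits in the same subjects.
- *The product wording spoils the change statements, or subjects rate one item of the kit.* None of the 13 comparative statements mentions a product. The protocol itself uses the singular for the whole system (Synopsis, Section 7.1), and Section 9.2.2 has subjects receive the system as a unit. Appendix 1 does speak to subjects of products in the plural, so the wording is loose, but misattribution is not shown.

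**Conclusion.** The point holds as a cheap improvement. Thirteen of 17 agreement statements are comparative with no stated reference, on a form used unchanged at four visits and with no baseline self-rating. From Day 28 on, the proportions in Section 14.2.4 cannot be read unambiguously as improvement since starting treatment, and a maintained benefit could appear to fade. This rests on the printed wording and on the assumption that some subjects would take a recent visit as their reference. How many would do so, and hence the size of the effect, cannot be derived from the protocol. No p-value or sample size is affected. The reason to act is that the ambiguity costs little to remove beforehand and cannot be resolved once the answers are collected. The product wording in four items is a minor clarification only.

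**What to change.** In both parts of Appendix 3, put the phrase *Compared with your skin before you started using the Obagi 360 system* in front of the existing instruction to rate agreement. As a minor clarification, replace *this product* with *the Obagi 360 system* in the satisfaction item and the three Yes/No items. Appendix 2 needs no change.

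The cost is a reprint of the questionnaire and an IRB submission, since Section 15.7 requires written approval of amendments by the IRB and the sponsor. If some subjects have already answered the unanchored form, record the form version and note it in the table. Visits, treatment, sample size and the planned summaries stay as they are.

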7.4 DURATION OF SUBJECT PARTICIPATION

The duration of the treatment is daily for 12 weeks. Subjects will be expected to come to the study center for the baseline visit and 4 additional study visits.

Subject's Self-Assessment of improvement Questionnaire (Appendix 2) will only be administered at Visit 2 and Visit 3

Subjects receive instruction during visit on how to apply study treatment product. The first application of study treatment product to the face will be applied at the conclusion of the Baseline visit as part of the Study Treatment Dispensing and Application Training.

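### The subject self-assessment has no response that means worse: all 17 agreement items in Appendix 3 are favourably worded, and the Appendix 2 No merges unchanged with worse

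*Protocol*

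**What the plan says.** The synopsis lists two criteria for evaluation: the investigator's skin grading and the subject's self-assessment.

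- **Appendix 3, Day 14, 28, 56 and 84.** Part 1 has eight agreement statements, such as "My skin texture has improved" and "I am satisfied with the overall results this product provides". Part 2 has nine, such as "My skin clarity has improved" and "My skin has a youthful glow/radiance". Each is answered on five levels from Strongly Agree to Strongly Disagree. Part 2 ends with three Yes/No questions on recommending, buying and continuing the product.
- **Appendix 2.** It asks "Have you noticed an improvement to your skin appearance", Yes or No, with a follow-up on speed of improvement for those who answer Yes. Under section 7.4 this form "will only be administered at Visit 2 and Visit 3", that is, at Day 14 and Day 28.
- **Timing.** Table 1 and section 11.3 place the self-assessment after baseline only.
- **Analysis.** Section 14.2.4 reports the proportion of subjects in each response category for each question and visit, without testing. For the investigator's grades, the synopsis plans a summary "categorized as the number and proportion of subjects 'Improved', 'Equal to' or 'Worse' than baseline"; section 14.2.3 and Table 4 do the same.

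**The concern.** A subject whose skin texture is unchanged and one whose texture has deteriorated can both truthfully disagree with "My skin texture has improved". The form gives neither of them an answer that states the direction. The Appendix 2 question goes further, because both must answer No.

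This is fixed by the forms, so later analysis cannot repair it: a response that was never offered cannot be recovered. What is at stake is a subject-reported table that shows how many subjects perceived benefit but cannot divide the rest into unchanged and worse. Breakouts are a concrete case. Breakout-prone subjects are deliberately recruited (section 8.1, criterion 3; section 7.2), yet the subject is asked only whether breakouts are less visible and less frequent. A subject with more breakouts has no answer that says so.

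**Working it through.** The plan states no figure on this point. The check is a count of the items, a look at what each answer can mean, and an illustration.

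**1. Items by wording (Appendix 3)**

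| Wording | Part 1 | Part 2 | Total |
|---|---|---|---|
| Favourable change | 6 (lines, firmness, tone, brightness, texture, resilience) | 7 (clarity, vitality, hydration, pores, breakout visibility, breakout frequency, smoothness) | 13 |
| Favourable present state | 1 (refreshed) | 2 (rejuvenated, glow/radiance) | 3 |
| Satisfaction | 1 | 0 | 1 |
| All | 8 | 9 | 17 |

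All 17 are favourably worded. None is worded unfavourably or offers two directions.

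**2. What the answers can mean**

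- *Appendix 2.* A subject who did not improve has one answer, No. Unchanged and worse are merged outright.
- *Appendix 3.* A subject who did not improve can tick Indifferent, Disagree or Strongly Disagree, and section 14.2.4 keeps these apart. The scale grades strength of disagreement, not direction of change. Indifferent is not defined as no change, and Strongly Disagree is not defined as worse.
- *Baseline.* With no baseline self-assessment, the 3 present-state items cannot be turned into change scores. The 13 change items would have no meaning at baseline in any case.

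**3. Illustration with 40 subjects (assumed counts, not from the protocol)**

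- Case A: 22 better, 8 unchanged, 10 worse.
- Case B: 22 better, 18 unchanged, 0 worse.

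Appendix 2, if every better subject answers Yes and all others No:

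- Yes = 22/40 = 55% and No = 18/40 = 45% in both cases.
- Net share better minus worse: A = (22 − 10)/40 = 30%; B = (22 − 0)/40 = 55%.
- Knowing only the 18 No answers, the share worse can lie anywhere from 0/40 = 0% to 18/40 = 45%, and the net share from (22 − 18)/40 = 10% to 55%.

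Appendix 3, if every better subject agrees and nobody else does:

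- The share agreeing is 55% in both cases.
- If unchanged subjects tick Indifferent and worse subjects Disagree, the three groups are 22, 8, 10 in A and 22, 18, 0 in B, so the full tables differ.
- If unchanged and worse subjects all tick Disagree, both cases give 22, 0, 18.

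The form does not say which mapping applies. Even where the tables differ, the reader has no defined way to turn the lower categories into a share worse.

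**The case against.** The strongest reply is that the instrument does what it is meant to do. The criterion is the subject's assessment of improvement, the objective in section 7 is to observe improvement, and no passage promises a subject-reported rate of worsening. Nothing is tested, so no inference depends on it. Worsening is looked for elsewhere: the investigator's grading runs in both directions, section 12.2 grades dryness/scaling, erythema, burning/stinging and itching, and section 12.1 has subjects asked non-directively at each visit about changes in their condition. The three Yes/No questions at the end of Part 2 also let a dissatisfied subject answer negatively.

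Most of this stands, and it limits the severity. It does not remove the point. The investigator's criterion is also framed as improvement, yet it is reported as improved, equal and worse. Investigator grades are not the subject's view, the tolerability list covers irritation rather than appearance, and an open adverse-event question does not systematically ask whether the skin looks worse.

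Some stronger readings are tempting, but the documents do not support them:

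- *Worse and unchanged subjects are recorded identically throughout.* This is true only of the Appendix 2 item. Appendix 3 has five levels that are reported separately, so its direction is ambiguous rather than merged.
- *All 17 items ask about improvement.* One asks about satisfaction and three describe a present state.
- *The two cases above must give the same Appendix 3 table.* They must do so only for the share agreeing, under the assumption stated there.
- *The absence of a control arm makes this uncorrectable.* A control group answering the same forms could not separate unchanged from worse either.
- *The study cannot show harm.* The limitation belongs to the self-assessment tables, not to the study.

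**Conclusion.** The point holds as a low-severity weakness of the questionnaires. None of the 17 agreement items, and not the Appendix 2 improvement item, has a response that denotes worsening. Appendix 2 merges unchanged with worse outright; Appendix 3 leaves the direction of disagreement undefined. One of the two evaluation criteria therefore cannot yield the proportion of subjects who feel their skin is worse.

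The count and classification come straight from the forms. How much information is lost depends on how many subjects worsen and how they use the lower categories. The protocol gives no figures for either, so the 40-subject example shows only the mechanism. No passage contradicts another here, and no planned test is affected.

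**What to change.** Keep the existing agreement items, and make these changes:

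1. Add to Appendix 3, at each post-baseline visit, one two-sided question: *Compared with before the study, my facial skin is: much better / better / the same / worse / much worse.*
2. In Appendix 2, replace Yes/No with *Improved / No change / Worse*, reword the question neutrally to match, and begin its follow-up with *If Improved* so that the branch on speed still works.
3. In section 14.2.4, summarize both as Improved, Equal and Worse, in line with the investigator's grades. State there that disagreement with the agreement items does not distinguish no change from worsening.

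The cost is one added question, one changed answer set with its follow-up, and a small addition to the tables, all on forms that subjects already complete. The downsides are a slightly longer form and a subject result that may look less favourable. If the forms can no longer be changed, the interpretation statement in section 14.2.4 is the minimum and needs no new data.
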